Disease/response assessment will be based on radiological tumor evaluation of neck, chest, abdomen, and pelvis by using IV (and oral, if indicated, per Imaging Manual) contrast enhanced CT/magnetic resonance imaging (MRI) and/or PET-CT imaging modalities at screening and at follow-up visits at the frequency described in the Schedule of Assessments ([Appendix 1](#)), and disease response will be based on the Modified Lugano Classification response criteria ([Appendix 5](#)). Please see [Table 7](#) for overall guidance on response assessment criteria based on Lugano Classification response criteria. In this clinical study, additional modifications to the Lugano Classification response criteria are incorporated per regulatory request to clarify rules for partial response (PR) assessment. These modifications highlight that morphologic (CT scan based) response will be the basis for PR assessment and not metabolic (FDG-PET scan) based assessment of response. Please see [Table 8](#) for details regarding combined response assessment criteria based on beforementioned modified Lugano Classification. For subjects followed by CT scans only, a bone marrow biopsy will be required to confirm a CR in a subject who achieve a morphologic CR by CT scan. To rule out a potential of false positive diagnosis of disease progression in ambiguous cases, it is highly recommended to repeat imaging assessments within 4-8 weeks after initial suspicion of PD. The Investigator's assessment of disease response will be used for subject management. For the final analysis of study efficacy endpoints, disease/response assessment will be performed by an IRRC blinded to Investigator assessment. For subjects with gastric MZL, endoscopy with biopsy must be performed to confirm CR.

Safety will be assessed by laboratory safety tests including hematology (complete blood count [CBC]), serum chemistry, and cytomegalovirus (CMV) using quantitative PCR; and clinical assessments including physical examination, vital signs, ECOG performance status, and 12-lead electrocardiogram (ECG). Adverse events will be graded according to National Cancer Institute Common Terminology Criteria for Adverse Events (NCI CTCAE) v5.0.

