# 7. RESPONSE ASSESSMENT AND STUDY ENDPOINTS

## 7.1. Overview

Efficacy assessments will be based on the Modified Lugano Classification response criteria ([Appendix 5](#)).

Response to treatment based on the Investigator evaluation of imaging tests will be the basis for subject management.

An IRRC composed of radiologists and oncologists will review all imaging tests, and clinical data if necessary, to determine disease response and progression. All radiographic images/scans will be sent by the study sites to the central imaging vendor and archived for potential future

evaluation (e.g., evaluation using Cheson criteria). The process for image collection and transmission to the central imaging vendor can be found in the Study Manual.

Tumor imaging (neck, chest, abdomen, and pelvis) should be performed by contrast-enhanced CT and/or FDG-PET scan. Because FL and MZL is typically (FDG)-avid, as per Modified Lugano Classification ([Appendix 5](#)) FDG-PET scan is the preferred method for disease/response assessment to confirm CR. If a combined/dual PET/CT scanner is the available modality, then the CT portion of a PET/CT may be used instead of a dedicated CT provided that the CT scan is performed with a high-resolution imaging quality to ensure optimal measurement for disease/response assessment. CT scans must be performed using intravenous (IV) contrast. For subjects who are intolerant to contrast agents, the CT scan will be performed with oral contrast or MRI scans will be used. If a PET/CT is not available or is not evaluable, bone marrow biopsy will be utilized to confirm a morphologic CR documented by CT scan. The imaging schedule is described in [Appendix 1- Response Assessment](#). In summary, imaging scans (CT scan or PET/CT scan) will be obtained with the following frequency:

- Every 2 months ( $\pm 7$  days) for the first 6 months on study
- Every 3 months ( $\pm 7$  days) for the next 12 months on study
- Every 6 months ( $\pm 14$  days) thereafter, starting with month 18

For subjects with gastric MZL, endoscopy with biopsy must be performed to confirm CR.

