## **8. STUDY PROCEDURES**

See the Schedule of Assessments ([Appendix 1](#)) for a detailed list of study procedures and assessments. Instructional details (where applicable) for procedures are contained in [Section 9](#).

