## 9.7. Laboratory Tests

Laboratory tests listed on the Schedule of Assessments ([Appendix 1](#)) will be analyzed at the investigative site's local laboratory and used in all safety analyses and response assessments (see [Appendix 5](#)); PK samples discussed in [Section 7.4](#) will be shipped to a central laboratory for analysis.

The following tests are to be performed:

- CBC with differential: white blood cell (WBC), ANC, red blood cell (RBC), hemoglobin (HGB), hematocrit (HcT), lymphocytes, eosinophils, monocytes, basophils, platelets, mean corpuscular hemoglobin (MCH)
- Serum chemistry: glucose, blood urea nitrogen (BUN) or urea, creatinine, sodium, potassium, chloride, calcium, alkaline phosphatase (ALP), AST, ALT, total bilirubin, total protein, albumin, LDH, phosphorus
- Coagulation: activated partial thromboplastin time (aPTT), prothrombin time (PT)/international normalized ratio (INR)
- Urinalysis: Dipstick or urine test (pH, specific gravity, glucose, ketones, blood, protein)
- Pharmacokinetic sampling (see [Section 7.4](#))
- Pregnancy test
- HIV testing
- Hepatitis B and Hepatitis C testing
- PCR test for CMV
- OI monitoring:
  - CD4 (for subjects with signs of infection)
  - Blood cultures if febrile neutropenia occurs, or when ANC is NCI CTCAE Grade 4
  - PCR for CMV (every cycle for first 6 months of treatment and every 3 months thereafter). If PCR test is positive for CMV, treatment should be delayed until recovery. Treatment of CMV should be initiated based on local SOC. Retreatment

with ME-401 will be allowed without dose reduction once PCR test for CMV is negative.

Subjects with identified risk factors will have the following tests performed:

- CD4 and CD8 count and ratio, c-reactive protein, blood cultures
- Any additional laboratory and diagnostic methods according to local SOC reported as unscheduled laboratory and diagnostic methods of assessment
- Radiological imaging (i.e., chest X-ray or CT scans)

Note: Treatment of the OI that started while on study should be based on local SOC.

- Bone marrow aspiration/biopsy: performed at screening at the discretion of the Investigator and repeated as indicated for subjects with known or suspected marrow involvement. Bone marrow aspiration/biopsy is to include surgical pathology, immunohistochemistry, and flow cytometry as per SOC. Bone marrow aspiration/biopsy is required to confirm a CR when a nodal CR is documented by a CT scan.

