- ff. **Bone marrow biopsy/aspirate** – Bone marrow biopsy/aspirate is obtained at screening and to confirm CR if PET scans were not performed or were not evaluable to assess bone marrow involvement. In addition, it can be performed as clinically indicated at the discretion of the Investigator.
- gg. **Endoscopy with biopsy** – For subjects with gastric MZL, endoscopy with biopsy to be performed to confirm CR.

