### **SELECTION OF NON-TARGET LESIONS**

Non-target lesions will be qualitatively assessed at each subsequent timepoint. All of the sites of disease present at baseline and not classified as target lesions will be classified as non-target lesions, including any measurable lesions that were not chosen as target lesions.

Examples of non-target lesions include:

1. All bone lesions, irrespective of the modality used to assess them
2. Lymphangitis of the skin or lung
3. Cystic lesions
4. Irradiated lesions
5. Measurable lesions beyond the maximum number of 6
6. Groups of lesions that are small and numerous
7. Pleural/pericardial effusions and/or ascites
  - a. Effusions, ascites, or other fluid collections will be followed as non-target lesions
  - b. At each assessment point, radiologists will check for the presence or absence of effusions/ascites. If there is a significant volume increase in the absence of a benign etiology, progression can be assessed
  - c. Significant new effusions, ascites, or other fluid collections, which are radiographically suggestive of malignancy should be recorded as new lesions and should be assessed

Response should be determined on the basis of radiographic and clinical evidence of disease. For subjects who achieve a CR by CT criteria, an FDG-PET will be performed. Assessment by PET should follow the criteria described by [Cheson 2014](#) which is summarized in [Table 7](#).

- Overall response should be determined based upon the Modified Lugano response criteria ([Table 8](#)).

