**Table 8: Modified Lugano Response Criteria**

Morphologic Response	Metabolic Response	Bone Marrow Biopsy	Prior Combined Response	Lugano Combined Response
NE/No CT	CMR			CR
	PMR			SD unless the previous CT scan indicated CR or PR, then combined response is PR*
	NMR			SD
	PMD			PD
	NE/No PET			NE
PD	CMR			PD
	PMR			PD
	NMR			PD
	PMD			PD
	NE/No PET			PD
SD	CMR			CR
	PMR			SD*
	NMR			SD
	PMD			PD
	NE/No PET***			SD
PR	CMR			CR
	PMR			PR
	NMR			PR*
	PMD			PD
	NE/No PET***			PR
CR	CMR			CR
	PMR			PR
	NMR			PR
	PMD			PD
	NE/No PET		No prior PET response	PR
	NE/No PET		No prior response and prior PET was negative	CR
	NE/No PET		SD	PR
	NE/No PET		PR	PR
	NE/No PET		CR	CR
	NE/No PET		PD and prior evaluable PET was not PMD	PR
NE/No PET***		PD and prior PET was PMD	NE	
NE/No PET	CR**		CR	

Abbreviations: BMB = bone marrow biopsy; CMR = complete metabolic response; CR = complete response; CT = computed tomography; NE = not evaluated; NMR = no metabolic response; PD = progressive disease; PET = positron emission tomography; PMD = progressive metabolic disease; PMR = partial metabolic response; PR = partial response; SD = stable disease

\* Lugano combine response criteria for this response combination has been modified per FDA request.

\*\* When a PET scan is not acquired or not evaluable, a bone marrow biopsy (BMB) is required to confirm a CR by CT. If no BMB is taken (and no PET can be acquired for this time point), the best possible overall response is a PR unless the prior overall response meets either criteria: prior overall response was CR or there was no prior overall response and the baseline/prior PET was negative.

\*\*\* When a timepoint does not have an evaluable PET scan, the morphologic response is not PD, and the most recent evaluable PET scan indicated a metabolic response of PMD, then the combined response will be NE. An improved combined response without evidence that the findings in the prior PET scan have resolved isn't justified. However, there is not PET-based evidence that the subject has continuing PD, so the response is designated as NE.

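### Protocol Section 9.7 requires a marrow biopsy to confirm any CR seen on CT, while every other rule in the protocol requires it only when there is no evaluable PET

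*Protocol*

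**What the plan says.** Protocol Section 9.7 (Laboratory Tests) states: "Bone marrow aspiration/biopsy is required to confirm a CR when a nodal CR is documented by a CT scan". Nothing in that sentence mentions PET.

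Four other places in the current protocol give the same biopsy a condition:

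- Section 5.1: "For subjects followed by CT scans only, a bone marrow biopsy will be required to confirm a CR".
- Section 7.1: "If a PET/CT is not available or is not evaluable, bone marrow biopsy will be utilized to confirm a morphologic CR documented by CT scan".
- Appendix 1, footnote ff (repeated under Table 1 of the SAP): the biopsy is obtained "to confirm CR if PET scans were not performed or were not evaluable to assess bone marrow involvement".
- Appendix 5, Table 8, footnote **: "When a PET scan is not acquired or not evaluable, a bone marrow biopsy (BMB) is required to confirm a CR by CT". The same footnote lets a CR stand with neither PET nor biopsy in two cases: "prior overall response was CR or there was no prior overall response and the baseline/prior PET was negative".

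The text of Appendix 5 makes PET, not biopsy, the next step: "For subjects who achieve a CR by CT criteria, an FDG-PET will be performed".

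Section 8 refers sites first to Appendix 1 for the list of procedures, then adds "Instructional details (where applicable) for procedures are contained in" Section 9.

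**The concern.** Two rules for confirming a CR stand side by side and give different instructions for the same subject. When CT shows a nodal complete response and PET shows a complete metabolic response, Table 8 assigns CR and stops. Section 9.7 still requires a biopsy before the CR is confirmed.

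Section 9 is where Section 8 places procedural detail, so a site coordinator or monitor could reasonably act on the sentence. Two things could follow. A subject might undergo an invasive biopsy that the response criteria do not need. Or the Investigator might withhold a CR that Table 8 already grants. Investigator-assessed CR rate is a secondary endpoint (Protocol Section 3.2), and SAP Section 7.2.1 summarizes agreement between the IRRC and the Investigator on best overall response. Uneven site practice could touch both.

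**Working it through.** The point rests on comparing text, plus one count of rows in Table 8. The plan states no figure to reproduce.

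**Step 1. When each rule asks for a biopsy to confirm CR**

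| Place | Condition on the biopsy |
|---|---|
| Section 9.7 | Nodal CR on CT; no PET condition |
| Section 5.1 | Subject followed by CT only |
| Section 7.1 | PET/CT unavailable or not evaluable |
| Appendix 1, footnote ff | PET not done or not evaluable |
| Table 8, footnote ** | PET not acquired or not evaluable, with two exceptions |

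Section 5.1 words its limit differently, but in substance it is also the case without PET. Section 9.7 is the only rule without a limit.

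**Step 2. Count the affected rows in Table 8**

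The block for a morphologic (CT) complete response has 12 rows. The combined response is CR in 4 of them:

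| Row | Biopsy needed in Table 8? | Biopsy under Section 9.7 as written? |
|---|---|---|
| Complete metabolic response on PET | No | Yes |
| No PET; no prior response and prior PET negative | No | Yes |
| No PET; prior combined response CR | No | Yes |
| No PET; biopsy supports CR | Yes | Yes |

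Rows giving CR without a biopsy: 4 − 1 = 3. Section 9.7 and Table 8 agree on one row and differ on three.

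**Step 3. Which rows matter in practice**

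The first row is the core of the conflict. Section 7.1 names FDG-PET as the preferred way to confirm CR, and Appendix 5 orders a PET after a CR by CT.

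The prior-CR row can recur in follow-up. Section 5.1 drops the PET requirement once CR is documented, so later scans may be CT only and may show a nodal CR again. This row is weaker evidence, because a CR already assigned arguably needs no second confirmation.

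**Step 4. Effect on the endpoints**

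- ORR counts CR and PR. Under Table 8 footnote **, a CT complete response with neither PET nor biopsy, outside the two exceptions, is at best a PR. That is still a response, so the primary ORR does not change.
- The IRRC assigns CR from the Appendix 5 criteria, not from Section 9.7, so its CR rate does not change.
- Investigator CR uses the same Appendix 5 criteria. It would change only if a site let Section 9.7 override Table 8.

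**Step 5. Who could be affected**

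Section 8.3 says enrollment is closed, with 121 FL and 32 MZL subjects treated on the intermittent schedule. Only those still having response assessments could meet the rule. The documents do not say how many that is.

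**The case against.** The strongest reply is that Section 9.7 was meant to describe only the CT route to CR. Table 7 supports this. Its CT-based column requires both nodal regression and a morphologically normal marrow, whereas its PET/CT column asks only that the marrow show no FDG-avid disease. On that reading, Section 9.7 says no more than that nodes alone do not make a CT-based CR. Further, Section 8 sends sites first to Appendix 1, where footnote ff carries the PET condition. Section 9.7 opens with a reference to Appendix 5, and Section 9.8 leaves biopsy to be done as suits the individual subject. A site would have to ignore several clear statements to go wrong. The row count measures table rows, not subjects. Finally, a protocol change needs regulatory and ethics review (Section 14) in a study planned for about 125 sites.

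Much of this stands. The CT-only reading is probably what was intended, no harm is prescribed, and the row count shows the extent of the textual conflict rather than its clinical frequency. A stand-alone amendment for this sentence would be hard to justify.

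The CT-only limit, however, is not written in the sentence. Neither the general reference to Appendix 5 nor the permissive wording of Section 9.8 cancels a specific requirement. A site that follows Section 9.7 exactly would biopsy a subject whose CR PET had already confirmed.

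**Conclusion.** The concern holds as a low-severity inconsistency in an operative instruction. Section 9.7 as written requires a biopsy in three of the four Table 8 CR rows for which Table 8 does not. The central case, a CT complete response confirmed by a complete metabolic response, is enough to establish the conflict even if the prior-CR row is set aside.

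The primary ORR and the IRRC-assessed CR rate are unaffected. What remains is a possible unneeded biopsy, or inconsistent recording of Investigator CR. Both depend on a site reading Section 9.7 literally and giving it precedence over Appendix 5. The number of subjects exposed cannot be derived from the documents.

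**What to change.** Add to the end of the last bone marrow sentence in Section 9.7: *if PET is not performed or not evaluable, per Appendix 5 Table 8*. The reference to Table 8 matters, because a bare PET condition would lose its two exceptions that allow CR with neither PET nor biopsy.

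The change is one clause. It adds no procedure, alters no analysis, and may spare some subjects a biopsy. Since any amendment needs regulatory and ethics review, the wording can go into the next amendment made for other reasons, with a clarification memo to sites in the meantime.

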## 9.8. Disease/Response Assessment

All CT scans, PET/CT scans, bone marrow biopsy, and laboratory evaluation will be completed as appropriate for individual subjects (scan should be conducted using IV, or oral if indicated, contrast enhanced CT/MRI and/or PET-CT imaging modalities). Efficacy assessments will be based on the Modified Lugano Classification response criteria in [Appendix 5](#).

All radiographic images/scans will be sent by the study sites to the central imaging vendor and archived for potential future evaluation. The process for image collection and transmission to the central imaging vendor can be found in the Study Manual.

For subjects with gastric MZL, endoscopy with biopsy will be performed to confirm CR.

## 9.9. Compliance Diary

A compliance diary will be provided to the subject at Cycle 1 Day 1 to record daily study drug administration. A new compliance diary will be provided at each study drug dispensing, according to the Schedule of Assessments ([Appendix 1](#)).

## 9.10. Dispensing of ME-401

Zandelisib (ME-401) is to be taken orally once a day at approximately the same time each day in accordance with the IS regimen (or CS dosing regimen if switched from IS after PD). ME-401 should be taken with a glass of water on an empty stomach (i.e., at least 1 hour prior to food intake or 2 hours after food intake). If a subject routinely experiences discomfort with dosing, he or she is permitted to take ME-401 with a light, non-fatty snack. On days with PK sampling, subjects should be instructed not to take study drug until after the PK sample is collected.

A compliance diary assessment and returned study drug accountability will be performed at each visit which includes study drug dispensing.

## 9.11. Managing the Impact of COVID-19 on Study Assessments

In light of the emerging COVID-19 pandemic, MEI acknowledges that at times it might not be feasible for ongoing study patients to visit a site due to local requirements to remain at home or existing health problems that increase their risk of infection with the novel coronavirus.

To allow subjects who are enrolled in the study to continue on treatment if it is deemed in their best interest, the following mitigation activities are allowed:

- If a subject cannot visit a site for investigational product (IP) dispensing, IP may be shipped directly to the subject or be dispensed to a family member if this is acceptable per institutional procedures and local regulations. If IP is shipped to a subject's home, this should be recorded in the source documents. If the subject will require additional compliance diaries, these should be included in the IP shipment. The site should follow up with the subject to ensure receipt of IP, enter the date of receipt in the source documents, and remind the subject to complete the compliance diary. Subjects should be instructed to return all used IP containers and compliance diaries to the site at their next study visit.
- Safety laboratory assessments may be conducted at any accredited laboratory. The Investigator should review laboratory results from tests conducted at another lab to determine if the subject should continue to receive ME-401. If safety laboratory assessments are conducted at a facility that is not listed on the site's form FDA-1572 or equivalent document, this should be recorded in the source documents. All laboratory results should be entered into the eCRF as soon as possible. Laboratory accreditation certificates and normal ranges should be collected whenever feasible for any alternative laboratories that are used.
- If an onsite study visit cannot be conducted as scheduled, site personnel should contact the subject by telephone or e-mail to assess his or her current status. Telemedicine visits are allowed if acceptable per institutional procedures or local regulations. Any new AEs or changes in AEs should be recorded in the source documents and entered into the eCRF as soon as possible. Any new concomitant medications or changes to existing concomitant medications should be recorded in the source documents and entered into the eCRF as soon as feasible. Any procedures that cannot be conducted remotely or at another facility, such as vital signs or physical examinations, should be documented in the source and will be recorded as protocol deviations.
- If the subject cannot have imaging for disease assessment conducted at the facility that is approved for the study, the imaging may be delayed or conducted at an alternate facility. If imaging is conducted at another facility, please obtain the imaging report and inform your CRA. If possible, images acquired at an alternate facility should be submitted to the central imaging vendor to determine whether the imaging results are of acceptable quality and may be used for disease assessment.
- If it is not feasible to obtain PK samples, please record this in the source documents. Any missing PK samples will be considered as minor protocol deviations as PK data are not critical for assessing safety or efficacy for this study.

If a study visit or procedure is delayed due to COVID-19, this should be recorded in the source documents. If an entire study visit is missed due to COVID-19, this should be recorded in the source documents. All missed or delayed study visits or procedures will be reported as protocol deviations.

